The secondary objective is to compare the effectiveness of Cognitive Processing Therapy and Accelerated Resolution Therapy in reducing depression symptom severity.

C. Tertiary Objective

The tertiary objective is to examine whether treatment effectiveness is reduced when patient preference for treatment is incongruent with their random assignment.

D. Exploratory Analyses

Exploratory analyses will be performed to examine whether demographic (e.g., sex, age, Veteran/Non-Veteran status) and other clinically-relevant variables (e.g., sleep quality, anger, pain, health care utilization) predict differential response and/or drop-out across treatment condition.

III. Study Design

This study will examine the effectiveness of Cognitive Processing Therapy (CPT) as compared to Accelerated Resolution Therapy (ART) and a Wait list (WL) control using a Randomized, Cross-Over Design with blinded assessment. 280 participants will be randomly assigned to receive ART, CPT or WL condition. Upon completion of the WL condition after 7 weeks, participants will be re-randomized to ART or CPT.

The primary outcome is improvement in PTSD symptom severity as measured by change on the Clinician-Administered PTSD Scale for DSM-IV or DSM-5 (CAPS-IV/ CAPS-5) after treatment. This primary outcome measure will be administered by post-doctoral fellows in psychology who will remain blinded to treatment condition. The

CAPS-IV and CAPS-5 will be administered at pre- and post-treatment, and 3-month and 1-year follow-up visits.

A. Study Population

Participants will be 280 male and female Veterans and civilians who meet criteria for PTSD, or subthreshold PTSD, due to any Criterion A traumatic event. Subthreshold PTSD occurs when a patient has a Criterion A traumatic event, and endorses symptoms in each of the PTSD Diagnostic Criteria (B-E), but falls below the number and/or severity of total Criterion requirements to meet criteria for a PTSD diagnosis. Inclusion and exclusion criteria and recruitment are described in Section IV.

1. Rationale for Inclusion of Non-Veteran participants

Civilians will be included in this study as they have different Criterion A traumatic events (e.g., non-combat). It is imperative to the primary study objective to assess the comparative effectiveness of CPT and ART across a variety of trauma(s).

B. Study Treatment Conditions

1. Treatment Conditions

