* Prior to the phone screen, participants will be asked to identify how they learned about the study and which site (UC or VA) they were referred from. Veteran participants may be seen at the Cincinnati VAMC or the UC Health Stress Center depending on their associated site. All civilian participants will be seen at the UC Health Stress Center.

D. Outcome Measures

The primary outcome is improvement in PTSD symptom severity as measured by clinically significant change on the Clinician-Administered PTSD Scale for DSM-IV or DSM-5 (CAPS-IV/CAPS-5).

A complete description of all of the outcome measures is in Appendix B.

E. Sample Size and Planned Statistical Analyses

1. Planned Statistical Analyses

The primary objective is to compare the effectiveness of CPT and ART in reducing the primary outcome -- PTSD symptom severity -- for Veteran and civilian patients with PTSD. We predict that CPT will be significantly superior to WL (and potentially superior to ART) in reducing PTSD symptoms post-treatment. To test this hypothesis we will use a 3 (Group: CPT, ART, WL) x 4 (Time: Baseline, Post-treatment) mixed-model ANCOVA covarying for baseline PTSD ratings. A significant omnibus interaction, and lower-order interactions, in the hypothesized direction will confirm this hypothesis.

The secondary objective is to compare the effectiveness of CPT and ART in reducing depression symptom severity. We predict that CPT will be superior to WL (and potentially ART) in reducing depression symptoms post-treatment. We will test this hypothesis with a mixed-model ANCOVA following the same analysis plan as for the primary objective.

The tertiary objective is to examine whether treatment effectiveness is reduced when patient preference for treatment is incongruent with their random assignment as we predict. To test this hypothesis, we will first categorize participants to a dichotomized preference group based on self-report. We will then perform a 2 (Group: Preferred Therapy, Non-preferred Therapy) x 4 (Time: Baseline, Post-Treatment, 3 Month, 1 Year) mixed-model ANCOVA covarying for baseline PTSD for both the primary (PTSD) and secondary (depression) outcome variables. A significant omnibus interaction, and lower-order interactions, in the hypothesized direction will confirm this hypothesis. Additionally, the primary and secondary analyses will be rerun covarying for preference to examine this variable's differential influence on CPT and ART outcomes.

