All phone screens will occur at the VA site. Study staff will contact potential participants, and prior to any screening data being collected participants will be asked to identify how they learned about the study and which site (UC or VA) they were referred from. Civilian participants can only be seen at the UC Health Stress Center. Once the participant's associated site is known, study staff will inform the participant that all study appointments will be held at their associated site and changing study sites during their involvement in the study will be prohibited. If the participant agrees with staying with their associated site, the phone screen will continue. If the participant does not agree, study personnel will explain the requirements for the study and refer the participant back to their original provider. All data collected during the phone screen will be stored on the appropriate secure network. Study staff will be equipped with access to both sites network, despite being housed at the VA site (e.g. UC laptop will be provided to store all UC participant's phone screen data). All data collected during the phone screen, including PHI, will be stored electronically on the appropriate site's secure network (e.g. PHI of VA participants will be kept on the secure VA Network; PHI of UC participants will be stored on the secure UC Network).

The phone screen will be used to determine if the participant might be eligible for the study by assessing inclusionary and exclusionary criteria, including patient current mood, behaviors, treatment, and medications (*See Forms: 01-Phone Screen, 02-Concomitant Medications, 03-Demographic Information, 04-Suicidal & Homicidal Screen*). All forms during the phone screen will be completed electronically in a database on the participant's designated site's secure network. If participants do not

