Assessment	Participant Payment (\$)
Baseline	70

Posttreatment*	75
3-month follow-up	85
1 year follow-up	100

*Individuals in the WL condition will receive two post-treatment assessments (one after WL period and one after completion of either CPT or ART following WL period), and will thus receive an additional \$75.00 for completion of the 2nd post-treatment assessment.

Participants randomly assigned to CPT or ART will receive up to \$330 in total compensation for their participation in this study. Participants randomly assigned to WL will receive up to \$405 in total compensation for their participation in the study.

Participants will be issued a debit card by the Greenphire ClinCard System. When a visit is completed funds will be approved and loaded onto the participants' card.

Participants will be issued one card for the duration of their participation. If a participant card is lost or stolen, they are instructed to call [contact]. An instruction sheet will be provided for further information. Greenphire and its Customer Support members will not have access to participant name or contact information; they will have a participant study ID number that will be provided to you by the study coordinator. Participants are able to use this study ID number to check the balance on their Greenphire debit card.

VII. Delivery of Therapy

A. Therapists: Two therapists at the UC Stress Center and 8 therapists at the Cincinnati VAMC, Trauma Recovery Center will perform all of the therapy. Therapists will be licensed clinical psychologists or licensed independent clinical social workers. Participants will be randomly assigned to therapist and then condition at both locations. Thus, all therapists will provide both therapies.

B. Training: [name] and three ART trainers will come to the Cincinnati VAMC for a 3-day ART training of the 10 therapists. [name] will ensure that therapists are appropriately trained in CPT.

C. Consultation: [name] and her team will provide weekly phone consultation in ART. All study therapists have already achieved CPT Provider status.

[name] will provide CPT consultation. Therapists will be approved as study therapists after [name] signs off on their abilities.

D. Digital Audio Recordings: All therapy sessions will be digitally audio recorded for later adherence review. See Data and Safety Monitoring section for more information.

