Appendix C. Randomization Tables.

1. University of Cincinnati, UC Health Stress Center Site

CPT/ART/WL Randomization Schedule

University of Cincinnati Site

Initial Randomization 1:1:1

block identifier	block size	sequence within block	treatment	provider	code	Participant ID (02-####)
5	48	1	WL		VJ8	
5	48	2	CPT	[name]	QD7	
5	48	3	CPT	[name]	XY8	
5	48	4	CPT	[name]	VN2	
5	48	5	CPT	[name]	AA2	
5	48	6	CPT	[name]	HH2	
5	48	7	ART	[name]	BR1	
5	48	8	ART	[name]	JC1	
5	48	9	ART	[name]	NB1	
5	48	10	ART	[name]	QT5	
5	48	11	WL		RG0	
5	48	12	CPT	[name]	MO9	
5	48	13	WL		AM0	
5	48	14	CPT	[name]	KX8	
5	48	15	WL		CC0	
5	48	16	ART	[name]	CU6	
5	48	17	ART	[name]	XX9	
5	48	18	CPT	[name]	PW2	
5	48	19	CPT	[name]	EK9	
5	48	20	WL		KQ3	
5	48	21	WL		PH6	
5	48	22	ART	[name]	EM1	
5	48	23	WL		DV2	
5	48	24	WL		EP0	
5	48	25	WL		SN1	
5	48	26	CPT	[name]	LY3	
5	48	27	CPT	[name]	GA9	
5	48	28	CPT	[name]	FN5	
5	48	29	WL		DP9	
5	48	30	CPT	[name]	GD7	
5	48	31	ART	[name]	EN6	
5	48	32	WL		ZF6	
5	48	33	ART	[name]	GF7	

5	48	34	WL		RF9
5	48	35	ART	[name]	HW4
5	48	36	ART	[name]	KU9
5	48	37	WL		NK4
5	48	38	CPT	[name]	RD5
5	48	39	WL		JM6
5	48	40	WL		EM0
5	48	41	ART	[name]	XZ3
5	48	42	CPT	[name]	YN8
5	48	43	ART	[name]	OX8
5	48	44	CPT	[name]	WU4
5	48	45	ART	[name]	EE5
5	48	46	WL		KG0
5	48	47	ART	[name]	NN5
5	48	48	ART	[name]	RJ2

Wait-List Randomization 1:1

block identifier	block size	sequence within block	treatment	provider	code	Participant ID (02-####)
6	16	1	CPT	[name]	VJ8-2	
6	16	2	ART	[name]	RG0-2	
6	16	3	CPT	[name]	AM0-2	
6	16	4	CPT	[name]	CC0-2	
6	16	5	CPT	[name]	KQ3-2	
6	16	6	CPT	[name]	PH6-2	
6	16	7	ART	[name]	DV2-2	
6	16	8	CPT	[name]	EP0-2	
6	16	9	ART	[name]	SN1-2	
6	16	10	ART	[name]	DP9-2	
6	16	11	ART	[name]	ZF6-2	
6	16	12	CPT	[name]	RF9-2	
6	16	13	ART	[name]	NK4-2	
6	16	14	CPT	[name]	JM6-2	
6	16	15	ART	[name]	EM0-2	
6	16	16	ART	[name]	KG0-2	

1. Cincinnati VA Medical Center, Trauma Recovery Center Site

CPT/ART/WL Randomization
Schedule
Cincinnati VAMC Site

Initial Randomization 1:1:1

block size	sequence within block	treatment	provider	code	Participant ID (01- ####)
192	1	WL		RL7	
192	2	CPT	[name]	QL9	
192	3	ART	[name]	YU4	
192	4	WL		YJ1	
192	5	WL		OS5	
192	6	CPT	[name]	UB6	
192	7	CPT	[name]	ZR3	
192	8	CPT	[name]	SC9	
192	9	ART	[name]	AR3	
192	10	CPT	[name]	CP5	
192	11	ART	[name]	CH6	
192	12	ART	[name]	KY7	
192	13	CPT	[name]	WC7	
192	14	WL		JE6	
192	15	ART	[name]	AL2	
192	16	CPT	[name]	LK7	
192	17	ART	[name]	SS5	
192	18	CPT	[name] [name]	YR1	

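### Site stratifies the randomisation but is in no planned model, so the exploratory Veteran/civilian predictor would absorb UC-versus-VA and therapist differences

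*Combined protocol and SAP*

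**What the plan says.** Section III.A.1 explains why civilians are enrolled: "Civilians will be included in this study as they have different Criterion A traumatic events (e.g., non-combat". It continues: "It is imperative to the primary study objective to assess the comparative effectiveness of CPT and ART across a variety of trauma(s".

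Site follows from civilian status. The footnote to Table 1.0 says "All civilian participants will be seen at the UC Health Stress Center", and section IV.E.1 repeats the rule: "Civilian participants can only be seen at the UC Health Stress Center". Veterans are not confined to one site: "Veteran participants may be seen at the Cincinnati VAMC or the UC Health Stress Center depending on their associated site". The expected number of Veterans at UC is not given.

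On staffing, section VII.A says "Two therapists at the UC Stress Center and 8 therapists at the Cincinnati VAMC, Trauma Recovery Center will perform all of the therapy". It adds that participants are randomised to therapist and then to condition, and that every therapist gives both therapies. Appendix C holds separate randomisation lists for UC and the VA, both for the initial 1:1:1 allocation and for the 1:1 re-randomisation after the wait list.

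Section II.D lists possible predictors of differential response and drop-out, among them "demographic (e.g., sex, age, Veteran/Non-Veteran status". Section III.E.1 makes no predictions for these analyses and describes hierarchical regressions for each treatment. The primary and secondary models adjust for baseline severity, with preference added in a rerun. Neither site nor therapist is named in any model, and trauma type is not a named predictor.

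**The concern.** No VA participant is a civilian, so Veteran status and site overlap heavily. They coincide completely if no Veteran enrols at UC. An analysis with Veteran status but not site credits to civilian status whatever differs between the clinics: case mix, referral route, setting, and the two UC therapists against the eight at the VA.

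This arises on either reading of the plan. If Veteran-by-therapy is tested, it picks up any site-by-therapy difference. If separate regressions are fitted for each treatment, as III.E.1 literally says, the Veteran coefficient is not a randomised contrast and picks up any UC-VA difference in response or drop-out within that arm.

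At stake is the interpretation of a secondary finding. A difference that belongs to one clinic could be read as a statement about civilians, the group whose inclusion III.A.1 specifically justifies.

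**Working it through.** **1. Reproduce the plan's total.** Counting the rows of Appendix C:

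| Site | Initial CPT/ART/WL | Re-randomised CPT/ART | Final per active arm |
|---|---|---|---|
| UC | 16/16/16 (48) | 8/8 (16) | 16 + 8 = 24 |
| VA | 64/64/64 (192) | 32/32 (64) | 64 + 32 = 96 |

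24 + 96 = 120 per active treatment, 240 in all, which matches III.E.2. UC holds 48/240 = 20% of the slots. Allocation is balanced within each site.

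**2. How much of a site difference reaches the Veteran coefficient.** Let *c* be the number of civilians, all among the 48 UC slots. Suppose UC and VA differ by δ (in therapy effect, or in response within one arm) and Veteran status has no effect. Civilians show the UC value. Of the 240 − *c* Veterans, 48 − *c* are at UC. With no site term, the Veteran-civilian contrast is expected to be δ × [1 − (48 − *c*)/(240 − *c*)] = δ × 192/(240 − *c*).

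- *c* = 12: 192/228 = 0.84 δ
- *c* = 24: 192/216 = 0.89 δ
- *c* = 36: 192/204 = 0.94 δ
- *c* = 48: 192/192 = 1.00 δ

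**3. What can be detected.** The detectable difference between two standardised CPT-ART effects (two-sided 0.05, power 0.80) is 2.80 × √(sum of 1/n over the four cells). Civilians and Veterans are each split equally between CPT and ART.

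| Civilians | Pooled, site ignored | Within UC only |
|---|---|---|
| 12 | 2.80 × √(2/6 + 2/114) = 1.66 | 2.80 × √(2/6 + 2/18) = 1.87 |
| 24 | 2.80 × √(2/12 + 2/108) = 1.21 | 2.80 × √(4/12) = 1.62 |
| 36 | 2.80 × √(2/18 + 2/102) = 1.01 | 2.80 × √(2/18 + 2/6) = 1.87 |
| 48 | 2.80 × √(2/24 + 2/96) = 0.90 | not estimable |

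The pooled column looks better only because it borrows VA Veterans, and so carries the site difference from step 2. Once site-by-therapy is in the model, the Veteran-by-therapy coefficient is the within-UC contrast. As a check at *c* = 24, the correlation between Veteran status and site is 0.667, the variance inflation is 1/(1 − 0.667²) = 1.80, and 1.21 × √1.80 = 1.62.

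**4. Oversampling.** The protocol allows up to 40 more participants (280) without saying at which site. If all 40 were civilians at UC, with every UC place civilian, there would be 88 civilians (88/280 = 31%). The pooled detectable interaction would be 2.80 × √(2/44 + 2/96) = 0.72, still fully aliased with site. If the 88 UC places were split evenly between Veterans and civilians, the within-UC figure would be 2.80 × √(4/22) = 1.19.

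**5. Trauma type as an alternative.** Section IV.A admits any trauma type at either site. With an ideal split of 60 in each trauma-by-therapy cell, the detectable interaction is 2.80 × √(4/60) = 0.72. Any imbalance makes it larger.

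**The case against.** The strongest reply is that little rests on this variable. Veteran status is one example in an illustrative list, in an analysis with no predictions. III.A.1 is an eligibility rationale, and the primary objective is a single CPT-ART comparison in a mixed population, which broad enrolment serves. Site-specific lists and therapists who deliver both therapies protect that comparison, overall and among civilians. All of this stands, and it keeps the point small. It does not justify leaving out of every model a factor the trial already randomises by.

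Four stronger readings are tempting, and the documents do not support them.

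- *Trauma type cannot be separated from site.* It is Veteran status that overlaps with site. Any trauma type is eligible at both sites, so Veterans at the VA may have non-combat trauma.
- *Veteran status is the planned test of the trauma question.* No section says so.
- *The protocol expects a standardised difference of 0.16 between CPT and ART.* Section III.E.2 gives that figure for CPT against PCT, says no direct CPT-ART data exist, and uses it conditionally.
- *The UC therapists are less prepared.* Section VII describes the same ART training, consultation and sign-off for all ten.

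**Conclusion.** The point holds as a low-cost improvement to the analysis plan, not as a flaw in the primary comparison. A Veteran-civilian difference analysed as planned would be largely confounded with site and therapist: under the 240-slot lists, 84% to 100% of a site difference carries over for 12 to 48 civilians. The only contrast free of site is within UC, with a detectable interaction of at least about 1.6 SD. It does not exist if no Veteran enrols there.

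The ceiling of 48 civilians belongs to the 240-slot lists and not to the target of 280. The number of Veterans at UC is not stated, so the results are given as a range. The detectable differences assume a continuous severity score with unit SD, full follow-up, no gain from covariates and no therapist clustering. Attrition or clustering would raise them, and a 50% response endpoint carries less information than the score. The carry-over figures assume a linear model, equal allocation and no other predictors related to site.

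**What to change.** In III.E.1:

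1. Include site (UC or VA) as a factor in the primary, secondary and exploratory models. In the per-treatment regressions, enter it alongside the demographic predictors.
2. Add site-by-therapy wherever Veteran-by-therapy is examined.
3. Report Veteran-civilian differences in therapy effect descriptively, within UC, giving the number of Veterans and civilians in each arm there. State that they cannot be attributed to civilian status apart from site and therapist, and add the same sentence to III.A.1.
4. Optionally, list index trauma type by therapy, with site in the model, as an exploratory predictor. This addresses the interest stated in III.A.1 more directly than Veteran status does. The plan describes no rule for choosing the index event or for coding combat, non-combat and mixed histories, so one is needed in advance. Low power should be acknowledged (0.72 at best with 240).

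Items 1 to 3 need wording only, with no change to recruitment, treatment or visits. Site as a two-level factor uses one degree of freedom. The real cost is a wider interval for the Veteran-by-therapy term (variance up 1.8-fold with 24 civilians at UC), which shows what the data can support. Item 4 also needs the coding work.

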Exploratory analyses will be performed to examine whether demographic and clinical variables differentially predict response and drop-out across treatment condition. Considering the exploratory nature of these analyses we make no predictions. However, we will use hierarchical multiple regression to examine the influence of demographics independent of the influence of clinical factors in predicting response (i.e., 50% symptom reduction) and drop out for each treatment. Based on the sample size estimate below, we will recruit a sample sufficient to include up to 24 predictors within these analyses – a more than sufficient number.

2. Sample Size Estimates

In order to estimate sample size, we used means and SDs from pilot data, prior studies from other groups (Frost et al., 2014; Kip et al., 2012; 2014) and a previously published study from our group (Suris et al., 2013) to determine the expected effect size (ES) for differences in PTSD symptoms across pre- and post-treatment (i.e. time). We also calculated treatment differences at the post-treatment time point only. We employed the ES metric delta (Δ) for mean time differences and Cohen's d for mean treatment differences. According to Cohen (1990), an ES $d = 0.2$ is considered small, 0.5 medium, and 0.8 large for behavioral research. Effect sizes within the large range are clinically relevant for behavioral research and even medium effect sizes should be “visible to the naked eye of a careful observer (Cohen, 1990).” Sample size estimates were then made using G*Power version 3.1 (Franz Faul, University of Keil, Germany). Using G*Power, we also estimated the a priori sample size required to identify the repeated-measures ANOVA interaction terms to be tested in the primary and secondary analyses.

ESs were large for active treatment differences across pre- and post-treatment times ($d = 1.04$ for CAPS reduction with CPT; $d = 2.02$ for PCL reduction in civilians with ART; $d = 1.28$ for PCL reduction in military with ART). To detect similarly large differences ($d_s > 0.8$) in PTSD severity means over time at $\alpha = 0.05$, power = 0.95 (to be conservative since there should be considerable power for these analyses), two-tailed in the proposed study would require at least a total $N = 32$ ($n = 16$ for each active treatment). A total sample size of $N = 152$ ($n = 76$ per active treatment condition) would be required

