to identify PTSD symptom reductions over pre-and post-treatment in the WL condition considering the medium ES.

ES was small for active treatment difference between CPT and PCT symptoms post-treatment ($d = 0.16$). No data directly comparing CPT and ART are available in the extant literature. To detect a similarly small difference ($d_s < 0.2$) in PTSD severity means post-treatment with $\alpha = 0.05$, power = 0.80, two-tailed in the proposed study would require at least a total $N = 706$ ($n = 353$ for each active treatment). Therefore, the proposed $N = 240$ would be insufficient to identify statistically significant differences between CPT and ACT post-treatment if we assume a similarly small effect size. The extant literature does not provide ES estimates between CPT vs. WL and ART vs. WL, but these ESs would be expected to be considerably larger than the CPT vs. PCT estimate.

In the absence of prior WL data with which to estimate ES, and considering that we intend to test interaction effects primarily, we estimate the necessary sample size to detect statistically significant Time x Treatment interactions across the entire power and ES range. Results indicate that for the primary analysis we will have sufficient power to detect even small effects with a total sample size = 246 ($n = 123$ per active treatment condition). For the secondary analysis we will have sufficient power to detect even small effects with a total sample size = 138 ($n = 69$ per active treatment condition).

It should be noted that the above calculations are based on simple contrasts between means and hypothetical power functions for the interaction term in repeated measures ANOVA, none of which include covariates. **These estimates are conservative in that inclusion of covariates, as expected in the final analysis, generally increases power and we intend to over-sample minimally to accommodate participant attrition, further assuring adequate power. *The total sample, then, will be N = 240, split equally between the two active treatments.*** This estimate, based primarily on repeated measure ANOVA, is very conservative as it provides a sufficient sample size to detect even small interaction effects. If needed, we propose oversampling by up to 40 participants to account for drop-outs from assessment or to bolster marginal effects.

F. Random Assignment:

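### The primary model gives two different time counts, does not say how the baseline covariate enters, and names no CPT-ART contrast to answer the primary objective

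*Combined protocol and SAP*

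**What the plan says.** Section III.E.1 makes CPT versus ART on PTSD severity the primary objective. The prediction attached to it has a different emphasis: "We predict that CPT will be significantly superior to WL (and potentially superior to ART) in reducing PTSD symptoms post-treatment". The test is a "3 (Group: CPT, ART, WL) x 4 (Time: Baseline, Post-treatment) mixed-model ANCOVA covarying for baseline PTSD ratings", and the decision rule reads "A significant omnibus interaction, and lower-order interactions, in the hypothesized direction will confirm this hypothesis". For depression, the secondary objective, the plan states: "We will test this hypothesis with a mixed-model ANCOVA following the same analysis plan as for the primary objective".

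The tertiary (treatment preference) model in the same section is a 2 x 4 design with all four times named, baseline included. It is a "mixed-model ANCOVA covarying for baseline PTSD for both the primary (PTSD) and secondary (depression) outcome variables".

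Section III.E.2 sizes the trial on the "repeated-measures ANOVA interaction terms to be tested in the primary and secondary analyses". It states that "for the primary analysis we will have sufficient power to detect even small effects with a total sample size = 246" and then "For the secondary analysis we will have sufficient power to detect even small effects with a total sample size = 138". It says that these calculations contain no covariates and that adding covariates should generally raise power. It plans 240 participants divided equally between the two therapies. It also discloses that 240 would be too few to detect a small post-treatment difference between them.

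Appendix C randomizes 1:1:1 at first, then WL participants 1:1 to CPT or ART. Section V.B says that the assessment after the 7-week wait becomes the WL participant's pre-treatment value.

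**The concern.** An analyst cannot fit the primary model from the sentence that defines it, for three reasons.

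- The number of times conflicts with the times listed.
- The same baseline score is a repeated outcome and a covariate. Depending on how the covariate enters, the Group x Time test is either a change-score test or an ANCOVA. Two analysts could follow the sentence and report different standard errors and p-values.
- The decision rule does not isolate CPT versus ART, which is the primary objective.

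A related gap is that no sentence says whether WL participants who are later re-randomized enter the CPT-ART comparison. Left open, the choice of model, contrast and analysis set for the primary result could be made after the data are seen.

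**Working it through.** **1. Time count, starting from the plan's own figures.** For the interaction in a repeated-measures ANOVA with k groups and m times, the noncentrality is lambda = f² x N x m / (1 - rho), with df1 = (k - 1)(m - 1) and df2 = (N - k)(m - 1). The documents do not give f, rho or power for this calculation. Assumed: f = 0.10 (a small effect), rho = 0.5, alpha 0.05, power 0.80.

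| Design | N needed | lambda at that N |
|---|---|---|
| 3 x 2 | 246 | 0.01 x 246 x 2 / 0.5 = 9.84 |
| 3 x 4 | 174 | 0.01 x 174 x 4 / 0.5 = 13.92 |
| 2 x 4 | 138 | 0.01 x 138 x 4 / 0.5 = 11.04 |

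One set of inputs gives both stated figures: 246 as 3 x 2 and 138 as 2 x 4. At rho = 0.3 a 3 x 4 design needs 243, close to 246, but 2 x 4 then needs 194, not 138. The 4 in the primary model is therefore probably a slip for 2. The 138 fits the layout of the tertiary model, although III.E.2 assigns it to the secondary analysis, which is said to follow the primary plan.

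**2. How baseline enters.** Let b be a participant's baseline and y the post-treatment score. In the repeated-measures ANOVA, Group x Time is tested on the within-person difference y - b.

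- Covariate as a main effect: it adds the same amount at both times, so it drops out of y - b. The test is the unadjusted change-score test.
- Covariate crossed with Time: y - b = time + group + delta x b + error. Moving b across gives y = time + group + (1 + delta) x b + error, which is ANCOVA on the post score.

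In post-SD units, with k now the post/baseline SD ratio, the change-score variance is (k² + 1 - 2 x rho x k)/k² and the ANCOVA variance is 1 - rho². Their ratio over an assumed range is:

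| k | rho 0.3 | rho 0.5 | rho 0.7 |
|---|---|---|---|
| 0.8 | 1.99 | 1.75 | 1.59 |
| 1.0 | 1.54 | 1.33 | 1.18 |
| 1.5 | 1.15 | 1.04 | 1.00 |

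As an illustration in power terms, take a CPT-ART difference of 0.36 SD. This is not a figure from the plan; it is roughly what 120 per therapy detects unadjusted with 80% power. With 80 per arm and k = 1, power is 0.48/0.62/0.83 for the change score against 0.66/0.74/0.89 for ANCOVA.

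**3. The decision rule when CPT equals ART.** Assume both therapies are 0.5 SD better than WL, with 80 per arm, equal SDs and the change-score test. The squared deviations of the three group means sum to 0.5² x 2/3 = 0.1667. Then lambda = 80 x 0.1667 / [2(1 - rho)] = 9.52, 13.33 and 22.22 at rho = 0.3, 0.5 and 0.7. On F(2, 237) the omnibus test is significant with probability 0.79, 0.91 and 0.99. At rho = 0.5, an assumed advantage of 0.3 SD gives 0.48 and 0.8 SD gives more than 0.999.

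**4. Numbers per therapy.** Counting Appendix C, the first randomization gives 16 + 64 = 80 per arm. Re-randomized WL participants add 8 + 32 = 40 per therapy. So 80 + 40 = 120 per therapy, and 2 x 120 = 240, if every WL participant goes on to treatment.

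**5. Tertiary model.** For the PTSD outcome, baseline is again both a Time level and the covariate. Simply deleting baseline from Time would not be safe, because a preference effect that stays constant over follow-up would then appear as a Group main effect, not as Group x Time. In a simulation with 60 per group, a constant 0.6 SD effect and all correlations 0.5 (assumed values), Group x Time was rejected in about 93% of trials with baseline kept and about 5% with it removed.

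**The case against.** - **The rule does what it says.** The stated prediction is CPT over WL. If both therapies beat WL, a significant interaction with CPT ahead of WL correctly confirms it. This stands. A reader might take the 0.79/0.91/0.99 as false-positive rates; they are not, because a true group difference exists. The remaining defect is that the confirmed statement is not the primary objective.
- **Lower-order interactions can be read as pairwise follow-up tests, including CPT-ART.** That is a reasonable reading, but no pair, estimate or interval is named, and a two-factor model has no interaction below Group x Time.
- **The covariate loss is conditional.** This stands. It arises only if baseline enters as a main effect, and it shrinks when post scores vary more than baseline scores. At k = 1.5, change-score power for 0.36 SD with 80 per arm is 0.60/0.73/0.89, close to ANCOVA. At the plan's d = 0.16 power is low either way: 0.14/0.17/0.26 against 0.18/0.21/0.29 with 80 per arm and k = 1.
- **The sizing match rests on assumed inputs.** This stands. Section III.E.2 says a range of power and effect sizes was examined. That 138 belongs to the tertiary layout is an inference.
- **The numbers per therapy agree.** This stands. A reader might see a conflict between 80 per arm in Appendix C and an equal split of 240 in III.E.2, but the two agree once re-randomized WL participants are counted. Section V.B also fixes their pre-treatment value. Only their place in the primary contrast is unstated.

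**Conclusion.** The concern holds as a specification gap that should be fixed. The time count is contradictory as written and is probably a slip for two. The entry of baseline is undefined; the choice changes the variance of the group comparison by a factor of 1.54/1.33/1.18 at correlations 0.3/0.5/0.7 with equal SDs, and by less if the post SD exceeds the baseline SD. Most important, the stated rule can be met when CPT and ART are identical, so it does not answer the primary objective.

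Two stronger conclusions may tempt a reader and are not supported. The first is that the primary test is invalid: the change-score test is valid and only forgoes the covariate gain. The second is that the sample size fails because that gain may be absent: the interaction sizing assumed no covariates. The power and probability figures rest on assumed effect sizes, correlations and SD ratios and allow for no attrition.

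**What to change.** In section III.E.1:

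- Correct the time count to two (baseline and post-treatment).
- Make the primary analysis an ANCOVA of post-treatment CAPS on group and baseline CAPS, so that baseline is only a covariate.
- Name CPT minus ART, with its 95% CI, as the test of the primary objective. Give CPT-WL and ART-WL, from the initial randomization only, as supporting contrasts.
- State whether re-randomized WL participants enter the CPT-ART contrast. If they do, use their 7-week CAPS as baseline, as section V.B already provides, and add a term for route of entry (direct or after WL).
- For the tertiary PTSD model, choose one of two forms. Either keep baseline in Time and drop it as covariate, or model the post, 3-month and 1-year outcomes with baseline and baseline x time as covariates. In the second form, test the group effect (the average, or the difference at a named time), not Group x Time alone.

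In section III.E.2, state the f, rho, power and layout behind 246 and 138, and the analysis to which each belongs.

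The cost is wording in the analysis plan. All the variables are already collected, and no visit, measure or participant is added.
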